ABSTRACT

Background:

After endotracheal intubation verifying the location of endotracheal tube is of utmost importance. Many methods have been applied but none is perfect. The standard practice is to use auscultation of chest with capnography. Ultrasound machines are now gaining popularity and their access extends from operation theatres, emergency rooms and even many primary health centres. Both capnography and ultrasonography are proven to be safe. This study aims to see if ultrasonography can also be made a routine method of endotracheal tube position confirmation inside operating theatres along with capnography.

Methods:

This was a prospective, observational study conducted at the Tribhuvan University Teaching Hospital (TUTH) and Manmohan Cardiothoracic Vascular and Transplant Center (MCVTC) operating rooms from January 2017 to July 2017. Ethical approval from the Institutional Review Board (IRB) of Institute of Medicine (IOM) and the Department of Anaesthesiology, Maharajgunj Medical College (MMC) was taken. Written informed consent was taken.

ASA I and II patients over 16 years of age were included in this study. Patients with difficult airway and anticipated difficult intubation, respiratory diseases, poor functional status, emergency case, and patients at risk of aspiration were excluded.

The diagnostic characteristics of real-time, suprasternal, transtracheal ultrasonography and capnography were tested by calculating their respective sensitivities, specificities, positive predictive values (PPV), negative predictive values (NPV), accuracies and likelihood ratios. Comparison of time taken for confirmation of endotracheal tube

position from the beginning of laryngoscopy, by ultrasonography versus capnography was done using t-statistics.

The degree of agreement of result between ultrasonography and capnography was tested with kappa statistics.

Results:

Out of the 95 patients studied, 11 had oesophageal intubation (Incidence of 11.57%). The overall accuracy of both ultrasonography and capnography was 96.84%. The sensitivity, specificity, PPV, NPV with their corresponding 95% confidence intervals (CI) for ultrasonography were 97.62% (91.66% - 99.71%), 90.91% (58.72% - 99.77%), 98.80% (92.67% - 99.81%), 83.33% (55.66% - 95.22%) respectively; and that for capnography were 96.43% (89.92% - 99.26%), 100% (71.51% - 100%), 100% (100% - 100%) and 78.57% (54.69% - 91.76%) respectively.

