The ideal method for confirmation of endotracheal tube placement should be fast, simple, reliable and safe.³ Visualization of passage of endotracheal tube through the vocal cords and waveform capnography showing sustained detection of exhaled carbon dioxide are the gold standard methods to confirm endotracheal tube placement.⁴ Capnography is the most important objective method to confirm endotracheal tube placement¹; and has been included into the ASA standards of monitoring.⁵ None of these methods including capnography fulfill all the credentials of an ideal method.³ No single method can be completely relied upon especially during emergency intubations.⁶ Most of these methods require bag ventilations which may lead to aspiration of gastric contents in the advent of oesophageal intubation. Objective monitors and techniques may not be widely accessible or may be difficult to learn and operate. Therefore adjunctive methods have to be added to the current standard practice to increase precision, reduce time and prevent hazards of oesophageal intubation.⁶

Exhaled CO₂ measurement

Capnometry is the measurement and numeric representation of the carbon dioxide (CO₂) concentration during inspiration and expiration.⁷ A capnograph, however, is a device that records and displays CO₂ concentrations as a function of time or volumes.⁸ A time capnogram is a continuous concentration–time display graphically of the CO₂ concentration sampled from a mixture of gases at a patient's airway during ventilation. The time capnogram is divided into four distinct phases⁷:

[figure not shown]

Fig.1. Normal capnogram showing a regular CO₂ waveform.^{7(p705)}

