be adjusted slightly to the left side of neck for proper visualization of the oesophagus including its posterior wall, prior to passing of the endotracheal tube.²⁰ Limitations of ultrasound also include wave scattering and acoustic artifacts generated in air-mucosa interfaces. Similarly presence of anatomical abnormalities in anterior neck and trauma or infection at the anterior neck, hamper the use of ultrasound at the suprasternal site.¹⁸

[figure not shown]

Fig. 7. Endotracheal tube in the oesophagus in ultrasound image. Presence of color Doppler ray outside of the trachea along with double tract sign.¹⁹

Another method described is to place the probe in transverse orientation at the level of vocal cords and see for fluttering at vocal cords or vocalis ligament in ultrasound as the endotracheal tube passes through. Tracheal ultrasound can also be done at the cricothyroid membrane level to see the placement of endotracheal tube.¹⁸ Additional sonographic way to identify endotracheal tube placement confirmation includes visualizing bilateral lung sliding while bagging the paralyzed patient.¹⁷

As opposed to capnography and auscultation, ultrasonography enables clinicians to identify oesophageal intubation prior to delivering ventilatory breaths through the endotracheal tube, potentially decreasing the risk of gastric insufflation and subsequent aspiration.

Tracheal ultrasonography is not affected by low pulmonary flow or bronchospasm unlike in capnography.^{1,17,20}

The current practice in anaesthesia is to use the combination of auscultation and capnography waveform observation for endotracheal tube confirmation in most centres including in IOM (Institute of Medicine), at TUTH (Tribhuvan University Teaching Hospital) and MCVTC (ManMohan Cardiothoracic Vascular and Transplant Center). But the capnography infrared sensor monitors are not widely available in Nepal. Also the matter of endotracheal tube confirmation is sensitive, it has to be done quickly prior to decreasing oxygen levels in the patient and aspiration of stomach contents into lungs has to be prevented. The practice of using capnography and auscultation requires repeated manual ventilations for endotracheal tube confirmation, and thus frequently falls short in this matter when compared to ultrasonography.^{3,6,21}

Rationale

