Pfeiffer et al³¹ did a prospective, observational study in 2010 comparing the time taken by bilateral lung ultrasound (observing lung sliding) with auscultation and capnography for verifying endotracheal intubation. Two separate investigators, one reading the capnograph and the other performing ultrasound, were blinded from each other while performing endotracheal intubation in a patient inside an operating theatre. Both methods were thus used at once in a patient. Both methods correctly verified endotracheal tube placement in all 25 patients. Comparing ultrasound with the combination of auscultation and capnography, median time for ultrasound was 40 seconds [Interquartile Range (IQR): 35 – 48 sec] vs. 48 seconds [IQR: 45 – 53 sec], $p < 0.0001$. Mean difference was -7.1 sec in favour of ultrasound (95% CI: 9.4 - 4.8 sec). Median time for auscultation alone was 42 sec [IQR: 37 – 47 sec], $p = 0.6$, with a mean difference of -0.88 sec in favor of ultrasound (95% CI: 4.2 – 2.5 sec). Thus they concluded that verification of endotracheal tube placement with ultrasound is as fast as auscultation alone and faster than the standard method of auscultation and capnography.

Gottlieb et al³² conducted a blinded, randomized trial in 2014 designing a 4 step technique of using ultrasound to check endotracheal tube position in two human cadaver models, one thin and the other obese. The technique in short was a transtracheal ultrasound at the transcricothyroid level with the probe tilted 30 degrees towards the left from midline in horizontal view. They would shake the endotracheal

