After intubation, the anaesthesia machine which was preset in volume control mode with tidal volume of 6ml/kg, respiratory rate of 26 breaths per minute (as used by Pfeiffer et al³¹ in their study), PEEP zero and inspiration:expiration ratio of 1:2; was then attached to the endotracheal tube via the anaesthesia machine circuit with ETCO₂ probe connected at the angle piece of the patient end of the circuit.

The ultrasound operator announced loudly as either “ultrasound positive” for tracheal intubation result, or “ultrasound negative” for oesophageal intubation result. The researcher noted down the time in the data entry proforma sheet (end point for ultrasonography).

The next anaesthesia resident (or anaesthesia assistant) meanwhile watched over the capnogram in the monitor. After 6 mechanical ventilations, he announced loudly as “capnograph positive” for tracheal intubation result, or “capnograph negative” for oesophageal intubation result. The researcher noted down the time in data entry proforma sheet (end point for capnography).

The supervising anaesthesia faculty then auscultated the chest in 5 areas in the order: right supramammary – left supramammary - left axillary – right axillary – epigastrium. The ultrasound operator performed bilateral lung ultrasound in second intercostal spaces in the mid-clavicular line and observed for lung sliding. The final endotracheal tube position in trachea was confirmed when there was presence of bilateral air entry on auscultation and lung sliding on ultrasound. In case of only unilateral air entry and unilateral lung sliding, the endotracheal tube was readjusted

for endobronchial intubation and reconfirmed again; the subject was not excluded from the study in the event of endobronchial intubation.

If there was absence of breath sounds with absence of lung sliding and bar-code sign²⁰ in the ultrasound in bilateral chest regions, reconfirmation further was done by the supervising anaesthesia faculty by performing repeat laryngoscopy and visualizing the position of endotracheal tube in relation to the vocal cords. This repeat reconfirmation was done because post-intubation bronchospasm or mucous plugging could also present with similar auscultation and lung ultrasound finding and thus negate the validity of the study. The supervising anaesthesia faculty would then reintubate himself if tube position in the oesophagus was seen during repeat laryngoscopy. The second intubation was not accounted for in this study.

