This study used both sidestream and mainstream capnographs. This was because of availability of different types of capnograph at the study sites. The details of sampling line delay are discussed later.

Ultrasonography vs Capnography

Both ultrasonography and waveform capnography were found to be good, reliable and fairly accurate diagnostic methods of confirming endotracheal tube position. Though ultrasonography and capnography were equally sensitive and capnography seemed more specific; the sensitivity, specificity, PPV, NPV of ultrasonography were comparable (statistically not different as seen by their confidence intervals) to waveform capnography.

The combination of ultrasonography and capnography increased precision (accuracy) over using either one of them in this study. Since the studies done previously had compared ultrasonography against capnography as the standard and thus calculated the sensitivity, specificity, PPV, NPV of ultrasound; these were not able to show if ultrasound had increased accuracy over using capnography alone.

Both of these methods are now known to be equally reliable. Hence in case of unmatched result given by these two methods in a patient, a third highly reliable method of confirmation has to be used because both ultrasonography and capnography have statistically not different false positive (1 – specificity) and false negative (1 – sensitivity) rates.

There was generally good agreement between the results produced by ultrasonography and capnography as shown by the kappa value of 0.749 with 95% confidence interval of (0.567 – 0.931). Other studies have shown a good or a very good agreement of these two methods by kappa statistics. The kappa value calculated by Adi et al³⁰, Chou et al²⁸, Karacebay et al²⁷ and Chintamani et al³⁴ were 0.85, 0.93 (0.84 – 1.00), 0.85 and 0.76 respectively.

Real-time, transtracheal, transverse suprasternal ultrasonography was significantly faster ($p = 0.011$) than capnography by 16.36 ± 3.23 seconds (mean \pm SD) in confirming endotracheal tube position in this study. The subgroup analysis between mainstream and sidestream capnographs also showed that the type of waveform capnograph device used did not affect the significant difference in time of ultrasound over capnograph in confirming endotracheal tube position.

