The sidestream capnograph at MCVTC had system response time of < 4 seconds, and that at TUTH had system response time of < 3 seconds. Adjusting for rise time of 200 milliseconds (the actual rise time of sidestream capnograph device used at TUTH; the rise time of that used at MCVTC was unknown), the transit time (delay time) would be in between 3 to 4 seconds in MCVTC sidestream capnograph and in between 2 to 3 seconds in TUTH sidestream capnograph. No delay was expected in mainstream capnograph device.

The median time taken for endotracheal tube confirmation by mainstream capnograph was 37 seconds and that by sidestream capnograph was 45.5 seconds. The combined median time taken for endotracheal tube confirmation by capnography was 42 seconds. The difference in time with ultrasonography was maximum of 19 seconds and minimum of 9 seconds while using mainstream capnograph, and maximum of 24 seconds and minimum of 12 seconds while using sidestream capnograph. These findings correlate to the delay time of sidestream capnographs as mentioned previously. Though theoretically the delay time should not have exceeded 4 seconds, the difference in median time for confirmation between these types of capnographs was 8.5 seconds. The median time for confirmation of endotracheal tube position in this study would be affected by the time taken by the anaesthesia resident for intubation. Thus difference in time for confirmation between the two types of capnographs could be greater or lesser than 8.5 seconds depending on the variability of time taken for intubation in this study.

Few studies have compared if ultrasound can be faster than capnography. Karacebay et al²⁷ found that dynamic transtracheal ultrasound at suprasternal level combined with lung sliding done by two separate operators simultaneously during intubation, was faster in average by 5.9 seconds than capnography for endotracheal tube confirmation. Pfeiffer et al³¹ found that lung ultrasound was in average 7.1 seconds faster than capnography in confirming endotracheal tube position.

The difference in time was greater in this study, likely due to use of sidestream capnograph. But as discussed earlier, this did not affect the significance in difference in time.

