Chintamani et al³⁴ in their study comparing ultrasound and capnography found mean \pm SD time for confirmation by ultrasound to be 12 ± 1.31 secs, and that by capnography to be 8.98 ± 1.04 secs. Their finding of capnography being significantly faster is debatable because they used transtracheal ultrasound at suprasternal level first in transverse view then in longitudinal view, followed also by scanning towards the left side of neck to align the area of oesophagus towards the center of probe. They also have not mentioned the criterion for capnography, whether $ETCO_2$ values were used or not, and the number of waves they counted for a result.

LIMITATIONS

1. This study used both sidestream and mainstream capnographs as per availability at the study sites. Sidestream capnographs have a delay time in reading exhaled CO₂, which does not occur in mainstream capnographs.
2. Different persons (anaesthesia faculties with training in airway ultrasound) performed ultrasound imaging in this study.
3. This study did not see if novice ultrasound operators could also confirm endotracheal tube position by ultrasound imaging earlier than capnography.

CONCLUSION

Ultrasonography and waveform capnography are equally reliable and accurate methods of confirming endotracheal tube position. Confirmation of endotracheal tube position by real-time ultrasonography is faster than capnography independent of the ultrasound operator. The combination of ultrasonography with capnography in practice will help reduce time and increase precision of confirming endotracheal tube position.

RECOMMENDATIONS

- Real-time transtracheal ultrasonography is safe and can be used as an alternate method of confirming endotracheal tube position in operating theatres.
- Using real-time transtracheal ultrasound can help confirm endotracheal tube position earlier than capnography.
- Using real-time transtracheal ultrasound will help avoid manual bag ventilations to confirm endotracheal tube position and can prevent aspiration of gastric contents into lungs in cases of oesophageal intubation.

REFERENCES

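### Any gain from ultrasound over current practice (auscultation plus capnography) cannot be estimated, because the comparator is capnography alone and auscultation is part of the reference

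*Combined protocol and SAP*

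**What the plan says.** The Abstract (Background) states: "The standard practice is to use auscultation of chest with capnography". The Introduction repeats this and names both study hospitals: "The current practice in anaesthesia is to use the combination of auscultation and capnography waveform observation for endotracheal tube confirmation". The Introduction also gives the motive: "Therefore adjunctive methods have to be added to the current standard practice to increase precision, reduce time".

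In Methodology (Materials and Methods), the ultrasound operator calls the result aloud. The capnogram reader calls the capnography result aloud after six mechanical ventilations. Only then does the supervising faculty member auscultate, while the ultrasound operator looks for lung sliding. The reference for a tracheal tube is: "The final endotracheal tube position in trachea was confirmed when there was presence of bilateral air entry on auscultation and lung sliding on ultrasound". Repeat laryngoscopy is reached only when breath sounds and lung sliding are both absent.

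The Discussion (Ultrasonography vs Capnography) reports: "The combination of ultrasonography and capnography increased precision (accuracy) over using either one of them in this study". The Conclusion carries this into practice: "The combination of ultrasonography with capnography in practice will help reduce time and increase precision of confirming endotracheal tube position". The Abstract's conclusion makes a similar statement. The three listed Limitations cover capnograph type, multiple operators and novice operators. None mentions the comparator or the role of auscultation.

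**The concern.** The document says that anaesthetists at these sites already use auscultation with capnography, and that an adjunct is needed on top of that. A reader who then meets a conclusion about what the combination will do in practice will take it as a gain over usual care.

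The design has no such comparison. One component of usual care is missing from the comparator and sits in the truth standard instead. Its separate results are not reported and its completion time was not recorded. A claim about changing practice would then rest on a comparison with only part of that practice.

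**Working it through.** **1. Reproduce the combined figure.** Inputs are Tables 8 and 9 and the Results text on the two methods together.
- Ultrasound: TP 82, FP 1, FN 2, TN 10; accuracy 92/95 = 96.84%.
- Capnography: TP 81, FP 0, FN 3, TN 11; accuracy 92/95 = 96.84%.
- Combination: all 84 tracheal tubes were identified by at least one method, and 10 of 11 oesophageal tubes by both. (84 + 10)/95 = 94/95 = 98.95%, which the document truncates to 98.94%. These counts correspond to calling a tube tracheal when either method does.

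**2. Split the gain over capnography alone into pairs.**
- Right under both: 81 tracheal + 10 oesophageal = 91.
- Wrong with capnography, right with the combination: 3 tracheal tubes.
- Right with capnography, wrong with the combination: 1 oesophageal tube.
- Check: 91 + 3 = 94 and 91 + 1 = 92.
- Exact two-sided McNemar p = 2 × [C(4,0) + C(4,1)]/2⁴ = 2 × 5/16 = 0.625.
- Sensitivity goes from 81/84 to 84/84; specificity goes from 11/11 to 10/11.
- Exact 95% intervals for accuracy: 94.3% to 99.97% for 94/95, and 91.0% to 99.3% for 92/95.

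**3. Try the comparison that the practice claim needs.** Let m be the number of errors that auscultation plus capnography would have made in these 95 patients. The accuracy gain of ultrasound plus capnography is 94/95 − (95 − m)/95 = (m − 1)/95. This is negative at m = 0, zero at m = 1 and positive from m = 2. The documents do not give m. Separate auscultation results are not reported, cases where breath sounds and lung sliding disagree are not defined, and no rule says how usual care combines auscultation with the capnogram. Because auscultation helps define the final position, its agreement with that position is partly built in.

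**4. Time.** The Methods and the proforma (Appendix C) have end points for ultrasound and capnography only. The 16.36 s mean difference is therefore a lead over capnography alone. The lead over completed auscultation plus capnography is unknown.

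**5. The cited 7.1 s.** The Discussion says: "lung ultrasound was in average 7.1 seconds faster than capnography in confirming endotracheal tube position". The Literature Review describes the same study's ultrasound as "faster than the standard method of auscultation and capnography": 7.1 s against that pair, and 0.88 s (p = 0.6) against auscultation alone. The Discussion then says that this study's larger difference is probably due to sidestream devices. Table 12 gives 14 s in the mainstream subgroup (n = 37) and 17.87 s in the sidestream subgroup (n = 58). The weighted mean, (37 × 14 + 58 × 17.87)/95 = 16.36 s, matches the overall figure. The excess over 7.1 s is 16.36 − 7.1 = 9.26 s overall and still 14 − 7.1 = 6.9 s with mainstream devices. Sidestream delay alone does not account for it. The comparators differ, and so does the technique (lung sliding there, transtracheal imaging here).

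**The case against.** The strongest reply is that the study never claims a measured improvement on usual care. The Objectives and Hypothesis compare ultrasonography with waveform capnography. The Rationale asks about ultrasound used along with capnography, and the Discussion benchmarks the combination openly against each method alone. Capnography is described as the most important objective method, so it is a defensible comparator. This stands: improvement on current practice is implied by the motivation and by the wording about practice, and is not reported as a result. It does not rescue the Conclusion, which drops the benchmark.

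A reader might go further and infer that the gain vanishes or reverses once auscultation is added. Setting auscultation equal to the final position, and calling a tube tracheal if either test does, makes usual care right in 95/95, one patient better than ultrasound plus capnography. The documents do not support this. The perfect score comes from incorporation, and they state no such rule for usual care. As an illustration, take the auscultation sensitivity of 94% and specificity of 83% quoted in the Literature Review (prehospital, non-arrest patients) and assume independence. The same rule then gives 3 × 0.06 + 11 × 0.17 = 2.05 expected errors and a gain of (2.05 − 1)/95 = +1.1 points. The sign is open.

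Nor is the drop in specificity an effect of changing the benchmark. Capnography alone was already 11/11, so the drop comes from how the two results were combined.

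On time, ultrasound was earlier than capnography in every case and auscultation followed the capnography call. In this sequence, ultrasound also preceded completed usual care. What is missing is the size of that lead.

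**Conclusion.** The point holds as a limit on the conclusion. The data speak to ultrasound against capnography read alone at six ventilations, before auscultation. They give no estimate, favourable or unfavourable, of accuracy or time gained over auscultation plus capnography. Against capnography alone, the accuracy gain is 2/95 = 2.1 points, made up of three corrections and one new error, and is compatible with no difference (p = 0.625). The faster ultrasound call is not in dispute, and Tables 8 and 9 stand.

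The three-and-one split assumes, as the Results say, that no tracheal tube was missed by both methods. The implied cross-table is 79 both tracheal, 4 ultrasound-only tracheal, 2 capnography-only tracheal and 10 both oesophageal. Observed agreement is 89/95 = 0.937, chance agreement is (83 × 81 + 12 × 14)/95² = 0.764, and kappa is 0.733, against the reported 0.749. The overlap should be checked in the raw data: one tracheal tube missed by both would make the combined figure 93/95.

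**What to change.** 1. In the Abstract's conclusion, the Discussion and the Conclusion, replace the statement about saving time and raising precision in practice. Limit it to capnography read alone at six ventilations, before auscultation. State that improvement over auscultation plus capnography could not be estimated. Beside 94/95, give the three corrected tubes, the one newly accepted tube and the specificity of 10/11 versus 11/11.
2. Add to the Limitations that auscultation formed part of the reference, was not timed, and followed the announced results.
3. In the Discussion, describe the 7.1 s as a lead over auscultation plus capnography, to match the Literature Review. Do not set it against 16.36 s as like for like, and do not attribute the excess to sidestream devices alone.
4. Optionally, tabulate the auscultation and lung-sliding entries from the proforma for the discordant and oesophageal cases. Label the table descriptive, subject to incorporation, and read after the index results were known. It would not give an unbiased estimate.

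The cost is wording, plus one small table if item 4 is done, with no new patients or procedures. The downside is a less favourable conclusion.
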